Published data supporting evaluation of the cAd3-EBO S comes from the Phase I, dose-escalation, open-label trial of cAd3-EBO (cAd3-EBO Z and –EBO S) performed by Ledgerwood, *et. al.* [17] Twenty healthy adults, sequentially enrolled in two groups of 10, received IM doses of 2×10^{10} particle units or 2×10^{11} particle units. No safety concerns were identified, although transient fever developed within 1 day after vaccination in two participants in the high dose group. Glycoprotein-specific antibodies were induced in all 20 participants, however the high dose group developed antibodies of higher magnitude and more frequent CD4 and CD8 T cell responses to vaccine antigen. The antibody levels of the high dose group were in the range associated with vaccine-induced protective immunity in NHP challenge studies, and the antibody responses were sustained to week 48. Other studies of cAd3-EBO and cAd3-EBO Z in U.S., Swiss and Malian adults showed the vaccines to be safe and immunogenic [16, 17, 19, 25]. Equivalent cAd3 Ebola Sudan WT GP doses will be tested in this slowly enrolling, staged, dose-escalation study.

It has been noted the 2×10^{11} PU dose of cAd3-EBO vaccine was associated with more reactogenicity than the 2×10^{10} PU dose, and the pattern is similar to other adenoviral vector vaccines. The first sets of clinical data suggest that about 70% of participants will have at least one systemic reactogenicity symptom. Reactogenicity typically occurs on the day of or day after vaccination and may include headache, malaise, myalgia, with a smaller percentage also experiencing fever or chills. When present, fever onset was within one day of vaccination and resolved within 24 hours of onset. A pattern of fever, occurring later than one day after vaccination or lasting longer than a day, may require evaluation for additional etiology [33].

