3.0 ENDPOINTS

3.1 Primary Endpoints: Safety

Assessment of product safety will include clinical observation and monitoring of clinical chemistry and hematology parameters. Safety will be closely monitored after injection and evaluated through 48 weeks after the study injection. The following parameters will be assessed:

- Occurrence of solicited local reactogenicity signs and symptoms for 7 days following the vaccination
- Occurrence of solicited systemic reactogenicity signs and symptoms for 7 days following the vaccination
- Change from baseline for safety laboratory measures
- Occurrence of adverse events of all severities through 28 days after the study injection
- Occurrence of serious adverse events and new chronic medical conditions through the last study visit

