5.3 Administration of the Study Injection and On-Study Assessments

Injections will be administered IM in a 1 mL volume by needle and syringe. It is recommended, but not required, that the injection be administered into the non-dominant arm. When choosing an arm for the injection, clinicians should consider whether there is an arm injury, local skin problem or significant tattoo that precludes administering the injection or will interfere with evaluating the arm after injection.

Following the study injection, participants will be observed for a minimum of 30 minutes. Vital signs (temperature, blood pressure, and pulse) will be taken 30 to 60 minutes post-injection (target of 30 to 45 minutes). The injection site will be inspected for evidence of local reaction during this period. In keeping with good medical practice, acute medical care will be provided to participants for any immediate allergic reactions or other injury resulting from participation in this research study.

5.3.1 7-Day Solicited Reactogenicity

Temperature and solicited local and systemic signs/symptoms will be recorded in the clinic prior to vaccination and at a minimum of 30 minutes post injection and then daily by the participant for 7 days.

Participants will be given a "Diary Card", a thermometer, and a ruler. The diary card will be used as a memory aid, on which the participant will record temperature, local and systemic symptoms and concomitant medications daily for 7 days after the injection. Participants will be trained to complete the paper diary card, how to use the thermometer, and how to measure injection site swelling and redness using the ruler. Completion of the diary card training will be noted in source documents. The written (paper) diary card will be transcribed into the study database and will be stored in the participant file for monitoring purposes.

The solicited signs and symptoms on the diary card (among others) will include: joint pain, malaise (feeling unwell), myalgias (muscles aches other than at injection site), headache, chills, nausea, and pain at injection site. Where multiple assessments are taken on the same day, participants will be requested to record the day's highest measured temperature and measurement of largest diameter for redness and swelling at the injection site. The completed diary cards are collected at the first visit following completion of the 7-day diary card (about 2 weeks after the injection).

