APPENDIX 10: DIARY CARD

[figure not shown]

RV 508 Participant Diary Card

**Makerere University Walter Reed Project
Kampala, Uganda**

**Version 1.5
03 March 2020**

Participant ID

Participant ID

General Symptoms Severity Scale

None= you have no symptoms

Mild= minimal symptoms; cause minimal or no interference with work, school, or self care activities.

Moderate=notable symptoms; required modification in activity; did not result in loss of work or cancellation of social activities

Severe = incapacitating symptoms; requiring bed rest and/or resulted in loss of work or cancellation of social activities.

[figure not shown]
[figure not shown]
[figure not shown]
For any Problems Call:

Injection Site Pain Severity Scale

How to Measure Swelling and Redness at the Injection Site

1. Determine the widest part (or diameter) of the area.
2. Using the ruler that the clinic staff gave to you, measure the widest part of the area in centimeters (cm) as shown on the pictures below. Each small hash mark on the centimeter ruler equals one tenth (0.1) of a centimeter.
3. Measure the swelling (raised area) and the redness (red area) separately and record each measurement on the diary card.

Please complete this diary in black or blue ink only

Participant ID

Day of Vaccination

Date: ____/____/____ (dd/mmm/yyyy)

The evening of the day of Vaccination:

Temp: _____ (oral, °C) Time Taken: _____ PM

If you have a fever and wish to take your temperature again, record your additional temperature:

Temp: _____ (oral, °C) Time Taken: _____ AM / PM (circle)

Temp: _____ (oral, °C) Time Taken: _____ AM / PM (circle)

Are you taking any medication? Yes No

If yes, please list medication(s):

Please use the symptom scale at the bottom of the page

Gen. Symptoms	None	Mild	Moderate	Severe
Joint Pain				
Feeling Unwell				
Muscle Aches (not at injection site)				
Headache				
Chills				
Nausea				

Injection Site Symptoms	None	Mild	Moderate	Severe
Local Pain				
Swelling Measure in cm	____. __ cm		Please record in cm, the largest width measurement of the swelling (Example: 2.5 cm)	
Redness Measure in cm	____. __ cm		Please record in cm, the largest width measurement of the redness (Example: 2.5 cm)	

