Symptoms Severity Scale**None** = no symptoms**Mild** = minimal symptoms; cause minimal or no interference with work, school, or self care activities.**Moderate** = notable symptoms; required modification in activity or medication; did not result in loss of work or cancellation of social activities.**Severe** = incapacitating symptoms; requiring bed rest and/or resulted in loss of work or cancellation of social activities.**For any problems call:** [REDACTED]**Injection Site Pain Severity Scale****None** = no pain**Mild** = minimal pain; no limitation of use of arm**Moderate** = notable pain; some limitation of use of arm**Severe** = extreme pain; complete limitation of use of arm

Participant ID

Day 1 after Vaccination

Date: ___/___/___ (dd/mmm/yyyy)

Temp: _____ (oral, °C) Time Taken: _____ AM / PM (circle)

If you have a fever and wish to take your temperature again, record your additional temperature:

Temp: _____ (oral, °C) Time Taken: _____ AM / PM (circle)

Temp: _____ (oral, °C) Time Taken: _____ AM / PM (circle)

Are you taking any medication? Yes No

If yes, please list medication(s):

Please use the symptom scale at the bottom of the page

Gen. Symptoms	None	Mild	Moderate	Severe
Joint Pain				
Feeling Unwell				
Muscle Aches (not at injection site)				
Headache				
Chills				
Nausea				

Injection Site Symptoms	None	Mild	Moderate	Severe
Local Pain				
Swelling Measure in cm	___ . __ cm		Please record in cm, the largest width measurement of the swelling (Example: 2.5 cm)	
Redness Measure in cm	___ . __ cm		Please record in cm, the largest width measurement of the redness (Example: 2.5 cm)	

Symptoms Severity Scale

None = no symptoms

Mild = minimal symptoms; cause minimal or no interference with work, school, or self care activities.

Moderate = notable symptoms; required modification in activity or medication; did not result in loss of work or cancellation of social activities.

Severe = incapacitating symptoms; requiring bed rest and/or resulted in loss of work or cancellation of social activities.

For any problems call:

Injection Site Severity Scale

None = no symptoms

Mild = minimal pain; no limitation of use of arm

Moderate = notable pain; some limitation of use of arm

Severe = extreme pain; complete limitation of use of arm

Participant ID

Day 2 after Vaccination

Date: ____/____/____ (dd/mmm/yyyy)

Temp: _____ (oral, °C) Time Taken: _____ AM / PM (circle)

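### The diary requires one temperature reading a day and prompts repeats only once fever is known, so short vaccine fevers can be missed and the fever row may be under-ascertained

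*Combined protocol and SAP*

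**What the plan says.** **Endpoint.** Section 3.1 lists as a primary safety endpoint "Occurrence of solicited systemic reactogenicity signs and symptoms for 7 days following the vaccination". Section 8.3.2 tabulates each sign or symptom by group and severity, counting each participant once at the worst recorded grade. Appendix 6 grades fever on measured oral temperature alone, starting at 38.0 °C.

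**Measurement.** Section 5.3.1 says that "the participant will record temperature, local and systemic symptoms and concomitant medications daily for 7 days after the injection". It sets no clock time and no number of readings per day. It asks for the day's highest temperature, but only "Where multiple assessments are taken on the same day".

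**Diary card (Appendix 10).** The Day 0 page asks for one temperature, headed "The evening of the day of Vaccination", with PM preprinted. Each page for Days 1 to 7 has one unconditional temperature line with AM or PM to circle. Every page then has two further lines, introduced by "If you have a fever and wish to take your temperature again, record your additional temperature".

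**Expected fever.** Section 1.2.2 reports of the two-vector vaccine: "When present, fever onset was within one day of vaccination and resolved within 24 hours of onset". Section 10.1.1 gives the same picture but says only that fever typically resolves in that time.

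**Other contacts.** Section 5.3 has a clinic temperature 30 to 60 minutes after injection. Day 1 contact may be by telephone. The first follow-up visit with scheduled vital signs is Day 3 (Appendix 1).

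**The concern.** The schedule of required readings is sparse in the period when fever is expected. After the clinic check, a participant must take only the Day 0 evening reading and one Day 1 reading before most vaccine fevers would be over. The Day 1 reading can be taken at any hour, so the gap between the two can be well over 12 hours.

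The repeat lines do not close this gap. They are offered to someone who already has a fever, which normally means that a reading has already shown one. A participant who measured normally in the morning and feels shivery in the afternoon is not asked to measure again.

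The error runs in one direction: a peak that is not measured can only lower the recorded maximum. The trial has no control arm and its purpose is to describe absolute rates by dose, so both the fever percentage and its grade distribution depend on capture. Solicited events must also be checked against the pause rules (Sections 7.2 and 7.5), and two of the three interim safety reviews follow the first three participants at a dose (Section 7.3).

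**Working it through.** **1. Required readings inside the expected window.** Setting Section 5.3 and Appendix 10 against Section 1.2.2:

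- 30 to 60 minutes after injection: clinic temperature, usually before any fever.
- Day 0 evening: one reading.
- Day 1: one reading, any time.
- Day 2: one reading, any time. It catches only fevers that start late on Day 1 or last long.

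**2. Share of fevers captured.** The documents give neither a duration distribution nor reading times, so these are assumptions:

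- injection uniform 09:00 to 15:00;
- Day 0 reading uniform 18:00 to 22:00;
- later single readings uniform 07:00 to 21:00;
- onset uniform 4 to 24 hours after injection;
- no extra readings;
- for the twice-daily schedule, a morning reading 06:00 to 09:00 and an evening reading 18:00 to 22:00 on Days 1 and 2.

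A fever counts as captured if any required reading falls between onset and onset plus duration. Simulated capture:

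| Fever duration | Diary as printed | Days 1–7 reading always in the evening | Morning and evening on Days 1 and 2 |
|---|---|---|---|
| 6 h | 36% | 20% | 50% |
| 12 h | 65% | 40% | 94% |
| 18 h | 86% | 70% | 100% |
| 24 h | 96% | 97% | 100% |

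A second set of assumptions (injection 09:00 to 14:00, Day 0 reading 18:00 to 21:00, three onset windows between 0.5 and 24 hours) gives 24–38%, 51–69%, 83–88% and 96–99% for the diary as printed. The twice-daily schedule then gives 46–51%, 95–96%, 100% and 100%. The pattern does not depend on one choice of timings.

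**3. Effect of readings prompted by symptoms.** If half of otherwise missed 12-hour fevers lead to a reading (an assumption), capture is 0.646 + 0.5 × 0.354 = 0.823, or about 82%.

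**4. What this does to a group of 20.** The plan's own figure comes first. For 0 of 20 the exact upper 95% limit is 1 − 0.025^(1/20) = 16.8%, as in Table 4. If capture is *s*, the limit on the true fever rate is 16.84% / *s*:

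- *s* = 0.96: 17.5%
- *s* = 0.82: 20.5%
- *s* = 0.65: 25.9%

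Take a true rate of 20%, which matches the two fevers among 10 high-dose participants in the earlier two-vector trial (Section 1.2.2). Then 20 × 0.20 = 4 fevers are expected. The expected recorded number is 4 × 0.96 = 3.8, 4 × 0.82 = 3.3 or 4 × 0.65 = 2.6.

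**The case against.** The strongest reply is that the size of the loss rests on durations that the documents do not contain. The only duration information is an upper bound of 24 hours, and at that bound the diary as printed misses about 4%. This stands: no single loss figure can be defended.

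Second, people measure when they feel feverish. They have a thermometer, spare lines on each page, and an instruction to record the highest reading where there are several. They also have a Day 1 contact and may come to the clinic at any time. This stands in part. It reduces the loss, but nothing on the diary page asks for a reading when symptoms appear.

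Third, at 20 per group the shift is small against sampling error. The exact 95% interval for 4 of 20 is 5.7% to 43.7%, and the expected shift in the examples above is at most about 1.4 participants. This is true, but sampling error can go either way and under-ascertainment cannot.

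Fourth, timing instructions may be given in diary training (Section 5.3.1) or in diary figures that are not reproduced here. That cannot be excluded.

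A reader might go further and infer that a primary fever rate is biased low by a known amount. The documents do not support this. Fever is one component of solicited systemic reactogenicity, and chills, feeling unwell, headache and muscle aches are solicited separately, so a febrile participant may still count as having a systemic reaction. Nor is every reading at a free time: the Day 0 reading is fixed to the evening, inside the expected onset window. Section 1.2.2 also reports no safety concern from the earlier trial, so its two fevers should not be called a signal.

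**Conclusion.** The point holds as a possible under-ascertainment of unknown size in one row of the reactogenicity table. It is not a demonstrated bias in the primary endpoint. The direction is certain, because a missed reading can only lower the recorded maximum.

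The magnitude depends on how long fevers last and how often participants measure unprompted. It ranges from about 4% of fevers missed at 24 hours to about 64% at 6 hours with no extra readings. At 12 hours it is about 35%, or about 18% if half of the otherwise missed fevers prompt a reading. The overall solicited systemic rate is less exposed than the fever row. No passages contradict each other here. This is an inexpensive improvement to measurement, not a correction that the trial depends on.

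**What to change.** **Change.**

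- On the Day 0, Day 1 and Day 2 diary pages, replace the conditional line with wording such as: *take and record your temperature whenever you feel hot, shivery or unwell*.
- On Days 1 and 2, ask for a morning and an evening reading. Keep one reading a day from Day 3.
- Match the daily recording sentence in Section 5.3.1 to this schedule.

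No new rule is needed on which reading is graded: Section 5.3.1 already asks for the day's highest and Section 8.3.2 already uses maximum severity.

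**Cost.** A diary reprint, a line in diary training and two more readings per participant. The thermometer and the extra temperature lines are already provided. The recorded fever rate may be higher than a once-daily schedule would show. A summary based on one reading per day, for example the evening reading, can be reported alongside, since the diary records the time of each reading.

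If the diary is not changed, the report should state that fever was ascertained from one required reading a day and that short fevers may have been missed.
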